8.3. Pharmacokinetic and Pharmacodynamics Endpoint

8.3.1. PK Endpoints

The following PK parameters (if possible) in Table 2 (SAD Cohorts) and Table 3 (MAD Cohorts) will be calculated for PF-06293620 from the serum concentration-time data using standard noncompartmental methods in Table 4 and [Table 5](#).

Table 4. PK Parameters for SAD Cohorts

PK Parameter	Analysis Scale	PF-06293620
AUC_{inf}^*	ln	A, D
AUC_{last}	ln	A, D
C_{max}	ln	D
T_{max}	R	D
$t_{1/2}^*$	R	D
V_z/F^* (for SC dose)	ln	D
CL/F^* (for SC dose)	ln	D
V_{ss}^* (for IV dose)	ln	D
CL (for IV dose)	ln	D
$AUC_{inf}(dn)^*$	ln	D
$AUC_{last}(dn)$	ln	D
$C_{max}(dn)$	ln	D

Key: A=analyzed using statistical model, D=displayed with descriptive statistics,
ln=natural-log transformed, R=raw (untransformed), *=if data permits

Table 5. PK Parameters for MAD Cohorts

PK Parameter	Day(s)	Analysis Scale	PF-06293620
AUC _τ	1, 57	ln	D
C _{max}	1, 57	ln	D
C _{min}	1, 57	ln	D
T _{max}	1, 57	R	D
CL/F	57	ln	D
C _{av}	57	ln	D
t _{1/2} *	57	R	D
V _Z /F*	57	ln	D
R _{ac}	57	ln	D
R _{ac,Cmax}	57	ln	D
AUC _τ (dn)	1, 57	ln	D
C _{max} (dn)	1, 57	ln	D
C _{min} (dn)	57	ln	D

Key: D=displayed with descriptive statistics,
ln=natural-log transformed, R=raw (untransformed), *=if data permits; dn = dose normalized.

8.3.2. PD Endpoints

Pharmacodynamic parameters including:

- Fasting plasma glucose, fasting plasma glucagon, fasting plasma GLP-1, 1,5-anhydroglucitol, fructosamine, HbA1c, AUC0-24hr of blood glucose; and
- Mean daily blood glucose levels (from fingerstick);
- Post-Prandial PD endpoints including: glucose, glucagon, insulin, GLP-1 and C-peptide excursions defined as AUC0-4 (change from baseline) in response to MMTT;
- Apo-B (MAD only).

The relationship between changes in the values of these biomarkers with the pharmacokinetics of PF-06293620 may be explored. Exploratory PK/PD modeling may be performed if visual examination of the data is suggestive of a relationship.

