The proposed PF-06293620 doses in the MAD portion were selected based on the preliminary PK/PD analysis and simulation from available data from the first 4 cohorts in the ongoing SAD study. Fixed dosages of 75, 150 and 250 mg Q4W were selected for this study to allow for adequate characterization of both the dose-response relationship for glycemic analytes (FPG, MMTT, mean daily glucose [MDG] and HbA1C), as well as to identify the maximum tolerated dose. Modeling suggests minimal accumulation ($R_{ac}=1.14$) of PF-06293620 after 3 dosages at 75 mg Q4W and approximately 1.4 and 1.6-fold increase in the exposure is predicted at 150 and 250 mg Q4W dosages, respectively. However, the predicted exposure at the highest dose (250 mg Q4W, ~3.1 mg/kg) is not expected to exceed the observed exposure at 6 mg/kg single-dose. The 6 mg/kg dose was found to be safe and well-tolerated. Guided by the dose-response relationship for baseline-adjusted FPG, the doses of 75 mg, 150 mg and 250 mg Q4W are deemed appropriate and adequate to allow for characterization of the dose-response relationship for PK, and PD changes. The 250 mg dose is expected to result in maximal fasting plasma glucose lowering. The 75 mg Q4W would approximately represent the dose for 50% maximal effect (ED50) and an intermediate dose of 150 mg Q4W was also proposed.

Proposed MAD doses, along with anticipated safety margins are listed in Table 4 below. The predicted human C_{max} and AUC_{tau} at the highest proposed dose would be approximately 122- and 20-fold below, respectively, the maximum observed exposures at 200 mg/kg (SC) in monkey in the pivotal, 3-month, toxicity study.

Table 4. Proposed PF-06293620 MAD Doses and Predicted Safety Margins based on the Exposures in Monkeys

Proposed PF-06293620 MAD Doses (mg)	Regimen	Predicted PF-06293620 Human Exposure		Projected Safety Margin*(fold)	
		C_{max} (μ g/mL)	AUC_{tau} (μ g*hr/mL)	C_{max}	AUC
75	Q4W	3.0	1471	653	126
150	Q4W	8.0	4486	245	41
250	Q4W	16.1	9448	122	20
TBD	TBD	--	--	--	--

Exposure at NOAEL doses (200 mg/kg) in monkeys:

IV: $C_{max} = 12,100 \mu$ g/mL; $AUC = 625,000 \mu$ g*hr/mL

SC: $C_{max} = 1,960 \mu$ g/mL; $AUC = 185,000 \mu$ g*hr/mL

*Margin calculated based on the NOAEL exposure/predicted human exposure

Source: Supportive Table 6 (RN909 Study B3501001: Preliminary PK report, May 2015)

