2.1.3. Exploratory Objectives

- To characterize the pharmacodynamics of PF-06293620.
- To characterize the effect of PF-06293620 on (post-prandial) glucose, insulin, GLP-1, C-peptide and glucagon excursions over 4 hrs following an MMTT.
- To evaluate changes in fasting lipid parameters.
- Additional exploratory objectives in the MAD portion will include 24 hour ambulatory blood pressure monitoring, and central review of ECGs .

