2.2.3. Exploratory Endpoints

- Change in pharmacodynamic parameters, including FPG, glucagon, GLP-1, 1,5-anhydroglucitol, fructosamine, HbA1c, AUC_{0-24hr} of blood glucose and mean daily blood glucose levels (from fingerstick).

- Post-prandial PD endpoints including glucose, glucagon, insulin, GLP-1 and C-peptide excursions defined as AUC₀₋₄ (change from baseline) in response to MMTT.
- 24-hour glucose AUC and weighted mean daily glucose.
- Lipid parameters (change from baseline) including: triglycerides, total cholesterol, HDL-C, and LDL-C.
- 24 hour ambulatory blood pressure monitoring, and central review of ECGs (MAD Cohorts only).

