8. ENDPOINTS AND COVARIATES

In general, Baseline is defined as the last available data prior to first study medication administration except for the following endpoints the Baseline is defined in Table 3.

Table 3. Baseline definition

Measurement	SAD	MAD
Fasting Weight	Mean of (Day -1, 1)	Mean of (Day -2, -1 and 1)
Temperature	Mean of (Day -1, 1)	Mean of (Day -2, -1 and 1)
Pulse Rate	Mean of (Day -1, 1)	Mean of (Day -2, -1 and 1)
Systolic Blood Pressure	Mean of (Day -1, 1)	Mean of (Day -2, -1 and 1)
Diastolic Blood Pressure	Mean of (Day -1, 1)	Mean of (Day -2, -1 and 1)
Fasting Plasma Glucose	Mean of (Day -1, 1)	Day 1 pre-dose
Fasting Glucagon	Mean of (Day -1, 1)	Day 1 pre-dose
Fasting GLP-1	Mean of (Day -1, 1)	Day 1 pre-dose

For triplicate ECG and vital signs readings, baseline is defined as the mean value of triplicate measurements prior to first study medication administration.

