10.2.4. Pharmacodynamic Analyses

PD biomarker data will include fasting plasma glucose, fasting glucagon, fasting GLP-1, 24-hr glucose profile (finger-stick), mean daily glucose profile, HbA1c, fructosamine, 1,5-anhydroglucitol, and glucose, insulin, C-peptide, glucagon and GLP-1 AUC after mixed meal tolerance test (MMTT, 4 hr). The relationship between changes in the values of these biomarkers with the pharmacokinetics of PF-06293620 may be explored. Exploratory PK/PD modeling may be performed if visual examination of the data is suggestive of a relationship.

The change and percentage change from baseline for PD biomarkers over the period of the study will be tabulated by treatment. The mean change from baseline values over time per cohort will also be tabulated. Data will be presented in tabular and graphical format and summarized descriptively. Descriptive statistics on change from baseline in fasting plasma glucose, fasting glucagon, fasting GLP-1, 24-hr glucose profile (finger-stick), HbA1c, fructosamine, 1,5-anhydroglucitol, and glucose, insulin, C-peptide, glucagon and GLP-1 AUC after mixed meal tolerance test (MMTT, 4 hr), and lipid parameters will be provided separately for each treatment and the pooled placebo group. The mean change from baseline over time with active treatment may be compared to the mean change from baseline over time with pooled placebo treated subjects using MMRM analysis with treatment as fixed effect, subject as a random effect, and baseline value as covariate adopting unstructured covariance structure. Figures of absolute values, change from baseline, and percentage change from baseline over time may be produced if needed.

The relationship between changes in the values of these biomarkers with the pharmacokinetics of PF-06293620 will be explored. Exploratory PKPD modeling may be performed if visual examination of the data is suggestive of a relationship.

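### The MMTT excursion endpoint, AUC0-4 as change from baseline, cannot by itself separate a changed meal response from a fasting shift; incremental AUC0-4 should be reported beside it

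*SAP*

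**What the plan says.** Protocol 2.1.3 sets the objective: "To characterize the effect of PF-06293620 on (post-prandial) glucose, insulin, GLP-1, C-peptide and glucagon excursions over 4 hrs following an MMTT". SAP 8.3.2 supplies the matching endpoint: "glucose, glucagon, insulin, GLP-1 and C-peptide excursions defined as AUC0-4 (change from baseline) in response to MMTT". Protocol 2.2.3 uses the same terms; its wording ends "GLP-1 and C-peptide excursions defined as AUC₀₋₄ (change from baseline) in response to MMTT". Neither document gives a formula for this AUC or says whether the pre-meal value is subtracted. SAP 10.2.4 plans descriptive change from baseline for "glucose, insulin, C-peptide, glucagon and GLP-1 AUC after mixed meal tolerance test (MMTT, 4 hr), and lipid parameters", with an optional MMRM that has the baseline value as covariate.

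On the meaning of baseline, SAP section 8 says: "In general, Baseline is defined as the last available data prior to first study medication administration". The exceptions in SAP Table 3 do not include the meal test. The only test before dosing is on Day -1 in every cohort (Protocol 7.4.1.2). Protocol 2.2.3 attaches the same parenthesis to another endpoint, "Lipid parameters (change from baseline) including: triglycerides, total cholesterol, HDL-C, and LDL-C", where it can only mean change from the study baseline.

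Samples are taken at 0 (fasting), 15, 30, 60, 120, 180 and 240 minutes. On meal-test days the time-0 sample also serves as the fasting glucose, glucagon and GLP-1 value (footnotes to both Schedules of Activities).

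Protocol 1.3.3 reports a fall in fasting glucose in the single-dose cohorts that flattened by 3 mg/kg, and for the multiple-dose part says: "The 250 mg dose is expected to result in maximal fasting plasma glucose lowering".

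**The concern.** AUC0-4 is the sum of two parts: four hours at the pre-meal level, and the area above or below that level after the meal. If drug lowers the fasting level, the first part falls even when the response to the meal is untouched. A dose-related fall in glucose AUC0-4 could then be read as a smaller meal excursion when it is only the fasting effect seen again. For glucagon, a higher fasting level on treatment would raise AUC0-4 and could be read as an exaggerated meal response.

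This matters because Protocol 1.3.1 intends the PD results to inform dose selection in later studies, Protocol 1.3.3 names the meal test beside fasting glucose as a dose-response measure, and SAP section 3 expands the 75 mg cohort for PD evaluation. What the meal test adds to fasting glucose is information on the meal response, and the plan has no summary that isolates it.

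**Working it through.** The documents give no effect size, SD or meal-test values for this endpoint, so there is no stated figure to reproduce. The profiles and shifts below are assumptions that show the mechanism; the weights and identities follow from the protocol's sampling times.

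**1. Weights.** The linear trapezoid at 0, 0.25, 0.5, 1, 2, 3 and 4 h gives weights 0.125, 0.25, 0.375, 0.75, 1, 1 and 0.5, which sum to 4.

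**2. Identity.** Let G0 be the same-day time-0 value. Then AUC0-4 = 4 × G0 + iAUC, where iAUC is the net area of (value − G0). If every sample falls by d, AUC0-4 changes by −4d and iAUC by 0.

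**3. Glucose example.** Assume fasting 180 mg/dL and meal increments of 0, 20, 45, 80, 85, 50 and 20 mg/dL.

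- iAUC = 5 + 16.875 + 60 + 85 + 50 + 10 = 226.9 mg·h/dL
- AUC0-4 = 4 × 180 + 226.9 = 946.9 mg·h/dL

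| Uniform fall (mg/dL) | Change in AUC0-4 (mg·h/dL) | % change | Change in iAUC |
|---|---|---|---|
| 20 | −80 | −8.4 | 0 |
| 40 | −160 | −16.9 | 0 |
| 60 | −240 | −25.3 | 0 |

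With assumed fasting levels of 150 to 210 mg/dL the absolute changes are identical, and the percentages run from −7.5 to −29.0 across the three shifts.

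**4. The two causes look alike.** With no fasting change, a cut in the meal response of 160/226.9 = 71% also gives −160 mg·h/dL. AUC0-4 alone cannot tell this from a pure 40 mg/dL fasting fall. The signs can even differ: a 40 mg/dL fasting fall with a 20% larger meal response gives −160 + 45.4 = −114.6 for AUC0-4, but +45.4 for iAUC.

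**5. Glucagon example.** Assume fasting 80 units and increments of 0, 10, 20, 20, 10, 5 and 0, so iAUC = 40 and AUC0-4 = 320 + 40 = 360. Doubling the fasting level with the same increment adds 320 (+89%); tripling it adds 640 (+178%). iAUC does not move.

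**6. Covariate adjustment.** The MMRM adjusts for the pre-treatment value. The shift arises after dosing, so this does not remove it.

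**7. Noise.** Assume independent error with SD s at each sample. The squared weights sum to 3.03, so the SD of AUC0-4 is 1.74s. For iAUC the time-0 weight becomes 0.125 − 4 = −3.875, the squared weights sum to 18.03, and the SD is 4.25s. The ratio is 4.25/1.74 ≈ 2.4. In the other direction, a day-to-day shift common to all samples, with SD u, adds 16u² to the variance of AUC0-4 and nothing to that of iAUC. The two variances are equal when 16u² = 18.03s² − 3.03s², that is u ≈ 0.97s.

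**The case against.** The strongest reply is that the plan has made no wrong choice. The word total appears in neither document, and the parenthesis could be taken as change from the pre-meal value. What can be shown is that the AUC is not fully specified, with the unadjusted form the better supported reading. That stands, and the point is worded accordingly.

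A reader might go further and infer that the endpoint cannot answer the post-prandial objective. The documents do not support this. The protocol summary and Protocol 1.3.1 name post-prandial glycaemia during the meal test as a glycaemic parameter, and AUC0-4 measures that properly.

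A reader might also infer that the AUC and the fasting endpoints are one result reported twice. No meal-test data are available to show it, and insulin and C-peptide have no separate fasting endpoint to repeat. The overlap is partial.

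Nor does the follow-up limit of three times baseline prove a dose-related rise in fasting glucagon: Protocol 7.4.1.1 says it was set from variability in placebo subjects. The glucagon arithmetic is therefore conditional on a shift.

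Fasting values are also summarised beside the AUC, and all data are listed, so the increment can be derived. This guards against misreading only in part. SAP Table 3 takes baseline fasting glucose from Day 1 (multiple-dose) or the mean of Days -1 and 1 (single-dose), not from the Day -1 time-0 sample alone. Subtracting four times the reported fasting change is therefore only approximate, and it gives no spread.

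The noise objection stands in full: with 6 to 16 active subjects per dose, replacing AUC0-4 by the increment would be a real trade-off.

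**Conclusion.** The point holds as a matter of interpretation and specification. On the best-supported reading, the excursion endpoint mixes the fasting level with the meal response, at 4 mg·h/dL per 1 mg/dL of uniform fasting shift. The protocol expects such a shift for glucose. The identity is exact for a uniform shift over the four hours; a non-uniform shift would divide between the two measures. The sizes of 80 to 240 mg·h/dL rest on assumed fasting falls of 20 to 60 mg/dL, because the documents give none. The factor of 2.4 rests on independent, equal error per sample.

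The endpoint is exploratory, no hypothesis is tested (SAP 6.1), and no error rate, sample size or listed dose-escalation criterion depends on it. Adding a companion summary is a cheap improvement; the documents do not support replacing AUC0-4.

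**What to change.** In SAP 8.3.2 and 10.2.4:

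- State the AUC method, and that change from baseline means change from the Day -1 meal test.
- Keep AUC0-4 as planned.
- Add net incremental AUC0-4, defined as AUC0-4 minus 4 h × the same-day time-0 value with negative areas kept, and summarise its change from Day -1 beside AUC0-4. Do this for glucose and glucagon, and optionally for insulin, C-peptide and GLP-1.
- For IV Cohort 5 on Day 1, add a footnote. Time 0 is drawn before dosing (Protocol 6.2.3) and precedes the meal by the infusion of roughly 60 minutes (Protocol 5.2.4), so the increment there mixes acute drug effect with meal effect.

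The cost is one derived variable per analyte and one further summary table, with no new samples. The drawback is the dependence on a single time-0 value, which is why the increment should be shown with AUC0-4 and not instead of it.

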8.3.3. Outcomes Research Endpoints

n/a.

8.4. Covariates

For all analyses of covariance, endpoints baseline measurements are to be used as a covariate. All other potential covariates may be introduced when appropriate.

9. HANDLING OF MISSING VALUES

Missing values will not be imputed.

10. STATISTICAL METHODOLOGY AND STATISTICAL ANALYSES

10.1. Statistical Methods

- All analyses will be presented by dose group.
- Placebo subjects will be pooled across cohorts for analysis and presentation purpose.
- Continuous data will be summarized using descriptive statistics: number of subjects (n), mean, standard deviation, standard error, median, minimum and maximum. 90% confidence intervals (CI) may be provided for pharmacodynamics endpoints.
- Categorical data will be described using frequencies and percentages. The denominator for all percentages will be the number of subjects for whom there are data in the cohort/treatment group within the analysis set of interest, unless otherwise specified. Counts of subjects with missing data will be presented if applicable.
- All data will be presented in listings. Data that will only be listed (not summarized) are specified in the analysis section.

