5.2.1. Drug Supplies

5.2.2. Formulation and Packaging

PF-06293620 will be provided as a solution for injection in a 20 mM histidine buffer at pH 5.8, at a concentration of 50 mg/mL. The drug product is supplied in 6 mL Type 1 clear glass vial sealed with a coated serum stopper and an aluminum seal, with a nominal fill volume of 4 mL

PF-06293620 will be shipped under refrigerated conditions (2-8°C) and should be stored under refrigerated conditions (2-8°C).

The placebo will be an appropriate sterile diluent solution supplied by the study site. The placebo formulation will be specified in the Dosage and Administration Instructions.

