5.2.4. Administration

Following an overnight fast of least 10 hours, subjects will receive study medication at approximately 0800 hours (plus or minus 2 hours). Qualified and trained investigator site personnel will administer study drug to subjects either by subcutaneous injection (SAD Cohort 1-4 and all MAD Cohorts) to the abdomen, or as a single IV infusion (SAD Cohort 5 only) by rate controlled intravenous infusion device over approximately 60 minutes. For subjects receiving two or more subcutaneous injections, study drug should be administered to two or more different quadrants of the abdomen; one or two injections per quadrant. Study staff should refer to the DAI for specific instructions on the handling and administration of study medication.

Subjects should take their metformin according to their usual time schedule and regimen. On Day 1 (all SAD and MAD cohorts), and on additional days where study drug is administered (MAD cohorts only) metformin should be taken prior to receiving study treatment.

Medication errors may result, in this study, from the administration or consumption of the wrong product, by the wrong subject, at the wrong time, or at the wrong dosage strength. Such medication errors occurring to a study participant are to be captured on the medication error case report form (CRF) which is a specific version of the adverse event (AE) page and on the SAE form when appropriate. In the event of medication dosing error, the sponsor should be notified immediately.

Medication errors are reportable irrespective of the presence of an associated AE/SAE, including:

- Medication errors involving subject exposure to the investigational product.
- Potential medication errors or uses outside of what is foreseen in the protocol that do or do not involve the participating subject.

Whether or not a medication error is accompanied by an AE, as determined by the investigator, the medication error is captured on the medication error version of the adverse event (AE) page and, if applicable, any associated adverse event(s) are captured on an adverse event (AE) CRF/DCT page.

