7.2.12. Injection Site Reaction Evaluation

Assessments made of the injection sites in the abdominal fat fold to monitor local tolerability to PF- 06293620 subcutaneous injections will be performed up to at least 2 hours following study drug administration at times specified in the [Schedule of Activities](#) section of this protocol. Site tolerability assessments should continue after each dosing day visit, only if injection site pain or ISR characteristics continue to persist. The assessments should continue at regularly scheduled visits until the symptoms resolve. Additional assessments should be performed as needed after the last assessment of 2 hrs post-dose on Day 1.

The injection sites will be assessed for erythema, induration, ecchymosis, injection site pain, injection site pruritus, or other observed characteristics after investigational product administration. The diameter of the affected area will be measured and the condition of the injection site will be recorded in the Subcutaneous Injection Site Assessment CRF. Any observed abnormality at the injection site will be judged by the investigator to determine whether a corresponding AE should be reported. Injection site reactions should be immediately photographed in color, with a scaled ruler placed by the reaction, and these photographs should be included in the subject's source documentation. Dermatologic photos will be redacted/remove any personal identifying information and will only contain the subject study ID. When appropriate, at the discretion of the investigator, a subject with an ISR may be referred for a dermatological consultation and a skin biopsy may be obtained for further histological examination of the ISR.

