9.6. Exploratory Analyses

Exploratory analyses will be conducted for SAD and MAD, respectively. The individual subject's change and percentage change from baseline for PD biomarkers over the period of the study will be tabulated by individual subject. The mean change from baseline values over time per dose group will also be tabulated. Data will be presented in tabular and/or graphical format and summarized descriptively. Placebo subjects will be pooled across all dose cohorts for the respective stages of the study, ie, SAD placebo subjects and MAD placebo subjects. To explore the treatment effect¹⁶, the mean change and percentage change from baseline over time with active treatment will be compared to the mean change and percent change from baseline over time with placebo treated subjects. Descriptive statistics on change and percentage change from baseline in fasting plasma glucose, post prandial glucose, insulin, C-peptide and glucagon AUC after mixed meal tolerance test (MMTT, 4 hr), 24-hr glucose profile (finger-stick), HbA1c, fructosamine, 1,5-anhydroglucitol; fasting

glucagon, total and active GLP-1 will be provided separately for each treatment and the pooled placebo group.

Exploratory PK/PD analyses may be conducted on relevant safety and PD endpoints as permitted by the data.

Data listings will be produced by study portion (SAD or MAD), subject, dose cohorts, visit date, and time.

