10.2.1. Primary Analysis

10.2.2. Safety Analyses

Subject evaluation groups will show end of study subject disposition and will show which subjects were analysed for pharmacokinetics (PK), and for safety (adverse events and laboratory data). Subject counts will be supplied for subject discontinuation(s) by treatment.

A summarization of demographic data will be provided for age, race, weight, and height. Each will be summarized by sex at birth in accordance with the sponsor reporting standards.

- Discontinuations, adverse events, laboratory data, vital signs, ECG and concomitant medication data will be summarized by treatment and in accordance with current Pfizer data standards. The adverse event risk difference will be summarized by treatment group. No p values and no multiplicity adjustments will be provided.

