10.2.2.6. Injection Site Reaction Evaluation

The injection sites were assessed for erythema, induration, ecchymosis, injection site pain, injection site pruritus, or other observed characteristics after investigational product administration. Injection site reaction evaluation will be summarized by dose and reaction response over time.

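### Placebo is pooled across cohorts regardless of route or injected volume, so placebo rates of injection-site and infusion-related AEs are diluted and, under stated assumptions, distorted by dose

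*SAP*

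**What the plan says.** The pooling rule is in SAP 10.1: "Placebo subjects will be pooled across cohorts for analysis and presentation purpose". SAP 7.3 applies the Safety Analysis Set, meaning everyone who received any study medication, to all analyses. Percentages use this denominator (SAP 10.1): "The denominator for all percentages will be the number of subjects for whom there are data in the cohort/treatment group".

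Two planned safety outputs are affected. SAP 10.2.2 says: "The adverse event risk difference will be summarized by treatment group". It names no comparator, so 10.1 makes it pooled placebo. SAP 10.2.2.6 says: "Injection site reaction evaluation will be summarized by dose and reaction response over time". It names no placebo contrast. The two outputs are linked by Protocol 7.2.12: "Any observed abnormality at the injection site will be judged by the investigator to determine whether a corresponding AE should be reported".

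The protocol limits the pooling (9.6, for exploratory pharmacodynamic analyses): "Placebo subjects will be pooled across all dose cohorts for the respective stages of the study, ie, SAD placebo subjects and MAD placebo subjects". The SAP does not repeat that limit, and SAP section 2 says the SAP takes precedence over the protocol's statistical text.

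On exposure, the drug is supplied "at a concentration of 50 mg/mL" (Protocol 5.2.2). SAD SC doses run from 0.3 to 6 mg/kg and Cohort 5 is given by infusion only. For subjects who need more than one SC injection, Protocol 5.2.4 says "study drug should be administered to two or more different quadrants of the abdomen; one or two injections per quadrant". Injections per dose, volume per injection and placebo volume are left to the Dosage and Administration Instructions, which are not part of these documents.

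**The concern.** A placebo subject who had no SC injection cannot have an injection-site AE, and one who had no infusion cannot have an infusion-related AE. Keeping such subjects in the denominator lowers the placebo rate for a reason unrelated to the drug.

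The second problem is volume. In the active groups it rises with dose. In a pooled comparator it is averaged over cohorts. If local reactions depend partly on how many injections a subject has, an active-minus-placebo difference then contains a procedural component that is negative at low doses and positive at high doses. That resembles a dose-response in local tolerability.

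Tolerability is part of the primary objective (Protocol 2.1.1), and the incidence of treatment-emergent AEs is a primary endpoint (Protocol 2.2.1). The distorted contrast would sit in a main safety table.

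**Working it through.** Neither document gives an injection count, a reaction rate or a placebo difference, so there is no plan figure to reproduce.

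**Volume, from the documents.** Mean weight over Protocol Table 1 is (9×89 + 6×93 + 6×77 + 6×90 + 9×88)/36 = 3153/36 = 87.6 kg. Volume = dose × 87.6/50, which gives 0.53, 1.75, 5.26 and 10.51 mL at 0.3, 1, 3 and 6 mg/kg. The ratio of highest to lowest is 6/0.3 = 20 at any fixed weight.

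**Assumptions, not in the documents.** Placebo volume equals the cohort's active volume. Each injection holds at most 2 mL. The reaction risk is p = 5% per injection on drug and placebo alike, so there is no drug effect. Planned numbers are used: 2 placebo subjects in each SAD cohort.

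The 2 mL figure fits the protocol's limits. At the Cohort 4 weight cap of 125 kg, 6 mg/kg is 15 mL, and four quadrants with two injections each allow 8 injections, so each must hold at least 15/8 = 1.875 mL.

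**Injections.** Volume/2 rounded up gives 1, 1, 3 and 6 for the four SC doses, and 0 for IV.

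**Incidence.** With independent injections, P(at least one reaction) = 1 − 0.95^k:
- k = 1: 5.0%
- k = 3: 1 − 0.857 = 14.3%
- k = 6: 1 − 0.735 = 26.5%

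The SC placebo pool is (5.0 + 5.0 + 14.3 + 26.5)/4 = 12.7%. With the 2 IV placebo subjects in the denominator it is 12.7 × 8/10 = 10.2%. Correlation within subject (ICC) of 0.3 uses a beta-binomial. ICC 1 treats reacting as wholly a subject trait.

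| ICC | 0.3 and 1 mg/kg | 3 mg/kg | 6 mg/kg | SC pool (8) | Pool with IV (10) | 6 mg/kg minus pool, SC only / with IV | 0.3 mg/kg minus pool, SC only / with IV |
|---|---|---|---|---|---|---|---|
| 0 | 5.0% | 14.3% | 26.5% | 12.7% | 10.2% | +14 / +16 | −8 / −5 |
| 0.3 | 5.0% | 10.8% | 15.7% | 9.1% | 7.3% | +7 / +8 | −4 / −2 |
| 1 | 5.0% | 5.0% | 5.0% | 5.0% | 4.0% | 0 / +1 | 0 / +1 |

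**Range.** For p from 2% to 20%, with IV placebo included, the 6 mg/kg excess is +7 to +41 points at ICC 0, +4 to +25 at ICC 0.3 and +0.4 to +4 at ICC 1. Without IV placebo it is +6 to +33, +3 to +19 and 0.

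**Infusion-related AEs.** If the rate among infused subjects is r on drug and placebo alike, the pooled SAD placebo rate is 2r/10 = 0.2r and the spurious difference is r − 0.2r = 0.8r. At an assumed r of 10% that is 10% against 2%, or +8 points.

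**MAD, own pool.** The final doses of 50, 75 and 150 mg are 1.0, 1.5 and 3.0 mL. At 2 mL that is 1, 1 and 2 injections per dosing day, or 3, 3 and 6 over three dosing days. With 2, 4 and 2 placebo subjects, p = 5% and ICC 0, the pool is (6×14.3 + 2×26.5)/8 = 17.3%. The differences are +9 points at 150 mg and −3 at 50 and 75 mg, a smaller spread than in SAD.

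**The case against.** The strongest counter-argument is that much of this depends on unseen instructions. A reader might infer that pooled placebo subjects are known to have had very different injection counts. The documents do not show that. They establish the 20-fold active-drug volume range and foresee multiple injections, but give no counts and no placebo volume. Blinded administration (Protocol 5.2.3) makes volume matching plausible, not certain.

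A reader might also infer that the injection-site table itself compares drug with a placebo group diluted by IV subjects. It names no such contrast. Its denominator is subjects with data, and Protocol 6.2.3 lists injection-site assessment for SC and infusion-reaction assessment for IV, so IV placebo should largely drop out there. The dilution remains in the AE tables, where every treated subject has data.

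A single pool across SAD and MAD is another possible inference. The SAP wording permits it, but the protocol's separate pools and the separate interim reporting of the two portions point the other way. The text is ambiguous, not decisive.

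Large artefacts require independent injections, a high reaction risk or small volumes per injection. At 1.5 mL, 8 injections hold 12 mL, which is 6 mg/kg at 100 kg, so heavier Cohort 4 subjects would exceed the protocol's limit. Correlated reactions roughly halve the effect or remove it.

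Finally, +14 to +16 points is about one subject in a planned group of six (16.7 points). SAP 10.2.2 gives no p values. The escalation criteria in Protocol 3.3 count events on active drug only, and Table 7 has no injection-site row, only a general discretionary one.

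All of this limits the size and reach of the point. None of it supplies the missing exception for route in SAP 10.1, or changes the direction of the volume effect under the stated assumptions.

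**Conclusion.** The point holds in two parts of unequal certainty. The route dilution follows from the SAP text alone: with planned numbers, 2 of 10 SAD placebo subjects cannot have an injection-site AE and 8 of 10 cannot have an infusion-related AE, yet they count in those AE denominators.

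The volume effect is conditional on matched placebo volume and on reactions that are at least partly per injection. Its direction is then predictable, but its size is not known from the documents. The 5% case is an illustration, not a forecast, and at ICC 1 with IV placebo excluded the effect vanishes. Excluding IV placebo does not settle the volume part at lower correlation: at 5% and ICC 0 the 6 mg/kg excess falls only from +16 to +14 points.

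Actual enrolment may differ from plan. Protocol Table 1 already shows 9 SAD placebo subjects for Cohorts 1 to 4.

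The consequence is a descriptive safety contrast that could be misread as dose-related local intolerance. The documents do not support reading it as a biased test or as a threat to dose escalation.

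**What to change.** Amend SAP 10.1, 10.2.2 and 10.2.2.6 as follows:
- For injection-site reactions and injection-site AE rows, use SC placebo only.
- For infusion reactions and infusion-related AE rows, use IV placebo only.
- State that SAD and MAD placebo are pooled separately, as in Protocol 9.6, and that this applies to safety as well.
- Show SC placebo by cohort, which stands in for volume, beside the pooled column.
- Report reactions per injection given where the CRF records the number of injections. Protocol 7.2.12 mentions the diameter and condition of the site but does not say that the count is captured.

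A formal contrast of each dose with its own cohort's placebo, or a subject-clustered model with injection count as covariate, is optional. With 2 placebo subjects per SAD cohort, and injection count nearly tied to cohort, neither would be precise.

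The cost is SAP wording and table programming, with no new data unless per-injection rates are wanted and the count was not recorded. The drawback is smaller denominators, 8 SC and 2 IV placebo subjects planned in SAD, and so less precise placebo rates.
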